7.5 Statistical Analysis Methodology

In general, data will be summarized using descriptive statistics by treatment group. Continuous variables will be summarized using the mean, standard deviation, median, minimum value and maximum value. Categorical variables will be summarized using frequency counts and percentages. All data will be presented in patient data listings. Any data excluded from the summaries and statistical analyses will be flagged accordingly. Baseline value is defined as the last valid value prior to the treatment, i.e. in other words, Baseline value is treatment specific value. If the data is missing at Baseline, then the Baseline will be imputed with the corresponding value at screening. Detailed methodology for summary and statistical analyses of the data collected in this study will be documented in a Statistical Analysis Plan (SAP). This document may modify the plans outlined in the protocol; however, any major modifications of the primary endpoint definition and/or its analysis will also be reflected in a protocol amendment.

7.5.1 Patient Demographics, Patient Disposition and Protocol Deviations

Descriptive statistics will be presented for continuous demographic variables and number and percentage will be presented for categorical demographic variables. Subject's disease characteristics will be summarized as applicable.

Patient accountability will be tabulated for all patients by summarizing the number of patients who are assigned to treatment, complete the study, or prematurely discontinue, and the reason for early discontinuation by treatment. A listing will be presented to describe dates of completion or early withdrawal and the reason for early discontinuation, if applicable, for each patient. Listings of data collected during the study, e.g., inclusion/exclusion criteria responses, study treatment administration will be provided.

The protocol deviations in the study will be evaluated on a case to case basis and will be categorized as major or minor. A major protocol deviation is defined as any deviation that may affect the efficacy outcome or the treatment of the subject. The number and proportion of subjects meeting minor or major protocol deviations will be summarized by treatment group. The data will also be listed. The protocol deviation criteria and detailed list of major protocol deviations will be mentioned in the statistical analysis plan.

Treatment duration and compliance will be descriptively summarized.

7.5.2 Prior and Concomitant Medications

Concomitant medications will be coded by using WHO dictionary. Concomitant medications will be summarized by ATC class and WHO preferred term by treatment, and overall, and will be listed for all subjects in the Safety Population

7.5.3 Analysis of Primary Endpoint

The primary objective of the study is to compute the survival of the patients without liver transplantation, renal failure or death during the treatment period of 96 hours. The number and proportion of patients surviving without liver transplantation, renal failure and/or death at the end of treatment period will be computed, 95% CI for the proportion of patients surviving without liver transplantation, renal failure and/or death will be computed based on Newcombe-Wilson score method.

The analysis of primary endpoint will be performed based on Full Analysis Set.

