| 
Primary Objectives
 | 
The primary objective is to evaluate the efficacy of Legalon® SIL in preventing hepatic failure and/or death resulting from amatoxin poisoning in a phase II clinical trial.
 |

| | |
|------------------------------------------|----------------------------------------------------------------------------------------------------------------------------------------------------------------------------------------------------------------------------------------------------------------------------------------------------------------------------------------------------------------------------------------------------------------------------------------------------------------------------------------------------------------------------------------------------------------------------------------------------------------------------------------------------------------------------------------------------------------------------------------------------------------------------------------------------------------------------------------------------------------------------------------------------------------------------------------------------------------------------------------------------------------------------------------------------------------------------------------------------------------------------------------------------------------------------------------------------------------------------------------------------------------------------------------------------------------------------------------------------------------------------------------------------------------------------------------------------------------------------------------------------------------------------------------------------------------------------------------------------------------------------------------------------------------------------------------------------------------------------------------------------------------------------------------------------------------------------------------------------------------------------------|
| 
Primary endpoints
 | 
The primary endpoint is the percentage of subjects treated under this clinical trial without morbidity (liver transplantation) and or mortality (death).
 |

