| | 
approximation, a sample size of 139, provides a two-sided 95% confidence interval for proportion of subjects not meeting the outcome of interest (liver transplantation and/or death) within a half width of 5% from the observed proportion at an expected proportion of 90%.
 |
| 
Statistical Methods
 | 
Demographic and Anamnestical Data:
 
All demographic and anamnestical data will be analyzed descriptively. For quantitative variables, the descriptive summary (means, medians, standard deviation, minimum and maximum) will be calculated. For qualitative data, the corresponding absolute and relative frequencies will be determined.
 
Efficacy Analysis:
 
The primary endpoint is the proportion of subjects treated with Legalon[®] SIL that do not exhibit morbidity (liver transplantation) and/or mortality (death).
 
Proportion of subjects not meeting outcome of interest (liver transplantation and/or death) will be determined. Furthermore, the corresponding 95% confidence intervals will be determined.
 
Sensitivity Analyses:
 
Subject survival rate without hepatic transplantation and/or death will be calculated for all subjects and for each stage of disease. Moreover, the corresponding 95% confidence intervals for the rate of survival will be determined. The survival time will be described by means of Kaplan-Meier estimates.
 
Secondary endpoint (efficacy):
 
 • All quantitative secondary endpoints will be analyzed descriptively. Means, medians, standard deviations, minimum and maximum will be calculated as measures of location and dispersion. • The time to normality for AST, ALT, bilirubin, PT/INR, and creatinine, if abnormal at presentation, will be determined for all subjects and for each stage of disease by means of Kaplan-Meier estimates. 
Additional summaries -- Assessment of Emergency Liver Transplantation Criteria in ALF due to Amanita Poisoning – using Ganzert’s and Escudie’s criteria. (13a.
 
 • Number (%) of subjects without hepatic transplantation by Ganzert’s intoxication (pre-treatment) • Elapsed days between amanita poisoning and start of treatment |

| | |

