3.2 Endpoints

3.2.1 Primary Endpoints

The primary endpoint is the proportion of subjects treated with Legalon® SIL that do not exhibit morbidity (liver transplantation and/or mortality (death)).

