7.3 Primary Endpoint

The primary endpoint is the proportion of patients treated with Legalon® SIL that do not exhibit morbidity (liver transplantation,) and/or mortality (death) at the end of treatment period (96 hours).

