7.5.4 Secondary/Sensitivity Analyses for Primary Endpoints

As a sensitivity analysis, the primary analysis will be repeated using the Per-Protocol Set.

In addition, the survival rates using Kaplan-Meier estimation method at 96 hours (end of treatment period) will be computed for the patients surviving without liver transplantation, renal failure or death. 95% CI will be computed for the survival rate by using Greenwoods formula. This analysis will be carried out using both Full Analysis and Per-Protocol Analysis sets.

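### The primary analysis counts an undefined renal failure as a failure event, but the primary endpoint and the sample size count only liver transplantation or death

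*Combined protocol and SAP*

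**What the plan says.** The endpoint is stated with two components in several places:

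- Section 7.3 takes the proportion of treated patients who "do not exhibit morbidity (liver transplantation,) and/or mortality (death) at the end of treatment period (96 hours".
- Section 3.2.1 has the same two components: "do not exhibit morbidity (liver transplantation and/or mortality (death".
- The synopsis endpoint is the percentage "without morbidity (liver transplantation) and or mortality (death".
- The synopsis efficacy analysis reads: "Proportion of subjects not meeting outcome of interest (liver transplantation and/or death) will be determined".
- The synopsis sensitivity analysis reads: "Subject survival rate without hepatic transplantation and/or death will be calculated for all subjects and for each stage of disease".
- Section 7.1 ties the precision of 139 subjects to transplantation and/or death, and section 7.6 reports the first 50 patients on the same two events.

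The analysis text has three components. Section 7.5.3 names renal failure three times: in its restatement of the study objective, in the proportion ("The number and proportion of patients surviving without liver transplantation, renal failure and/or death at the end of treatment period will be computed"), and in the 95% confidence interval by the Newcombe-Wilson score method. Section 7.5.4 names it once more, for Kaplan-Meier rates at 96 hours that "will be computed for the patients surviving without liver transplantation, renal failure or death".

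**The concern.** The primary analysis should estimate the primary endpoint. Here a programmer who follows 7.5.3 codes three failure events, and a reader of 7.3 expects two. The per-protocol repeat and the Kaplan-Meier analysis in 7.5.4, and the repeats by severity stage in 7.5.6, inherit the mismatch.

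The added event also cannot be applied as written, because no criterion for it is given. In an open-label, single-arm trial whose first 50 outcomes are already reported, the rule for classifying renal states could then be settled after outcomes are known. A final three-event result would not be comparable with the two-event interim result from the same trial, and the sample-size statement does not cover it.

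**Working it through.** **1. Event sets side by side**

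| Place | Transplantation | Death | Renal failure |
|---|---|---|---|
| Synopsis: endpoint, efficacy, sensitivity, sample size | yes | yes | no |
| 3.2.1 | yes | yes | no |
| 7.1 | yes | yes | no |
| 7.3 | yes | yes | no |
| 7.6 (interim) | yes | yes | no |
| 7.5.3 (three times) | yes | yes | **yes** |
| 7.5.4 (once) | yes | yes | **yes** |

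The two sets give the same proportion only if no patient has renal failure without also dying or being transplanted.

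**2. Is renal failure defined?** Section 2.2 describes it clinically under Stage III, as hepatorenal or directly nephrotoxic, with possible severe oliguria or anuria. The paragraph on kidney function says that prerenal azotemia at presentation is common and usually reversible, and it also describes direct toxicity and a later hepatorenal syndrome. BUN, creatinine and GFR are scheduled in Table 1. No threshold, duration or dialysis criterion is given, and nothing says whether a state present at baseline counts.

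**3. Reproducing the sample size.** Inputs from 7.1: expected proportion 0.90, half width 0.05, two-sided 95% interval, normal approximation.

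n = 1.96² × 0.90 × 0.10 / 0.05² = 138.3, rounded up to 139. This matches the plan.

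Half width at 139 = 1.96 × √(0.90 × 0.10 / 139) = 4.99 points.

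The arithmetic is correct, and it is stated for the two-event outcome.

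**4. Interim result.** In 7.6, 42/50 = 84.0%. The exact (Clopper-Pearson) interval is 70.9% to 92.8%, as stated. This too is for two events.

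**5. Effect of the third event.** One patient of 139 is 100/139 = 0.72 points. The documents give no rate of renal failure without transplantation or death, so the rows below 90% are assumptions for illustration only.

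| Event-free proportion | Patients moved of 139 | Half width, normal approximation | Wilson interval (half width) |
|---|---|---|---|
| 90% (plan) | 0 | 4.99 | 83.9 to 94.0 (5.04) |
| 88% (assumed) | 0.02 × 139 = 2.8 | 5.40 | 81.6 to 92.4 (5.43) |
| 85% (assumed) | 0.05 × 139 = 7.0 | 5.94 | 78.1 to 90.0 (5.93) |

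Half widths are in percentage points. The Wilson columns apply the score method at exactly 90%, 88% and 85% with n = 139.

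**The case against.** The strongest reply is that the shift may be negligible. Section 7.6 says that the 42 interim successes recovered completely and attributes the 8 failures to progressing liver and renal failure, so renal failure appears there among patients already counted as failures. Only 11 of 50 patients had any adverse event. If all 8 failures are among those 11 (an assumption), at most 11 − 8 = 3 successes had an event of any kind. This stands as evidence that new-onset renal failure alone was rare. It does not bound the effect. Section 6.4.1.1 sends screening findings to medical history, so renal impairment at baseline is outside the adverse-event count, and 7.5.3 does not say whether such cases count.

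A second reply is that precision is a weak argument. At the interim two-event rate of 84%, the half width at 139 is 1.96 × √(0.84 × 0.16 / 139) = 6.09 points, wider than either illustration above. This is right: deleting renal failure does not secure a 5-point half width. It only makes the events in the precision statement match the events analysed.

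Third, section 7.5 leaves detailed methods to a separate SAP, so the absence of a definition can be asserted only for the supplied text. That does not cure the conflict. The same section says that major changes to the primary endpoint or its analysis will also appear in a protocol amendment.

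Finally, the plan states no hypothesis test or success threshold that the extra event could reverse, and the stated endpoint remains computable from the same data. Both points are true, and they place the fault in the written analysis and not in data collection.

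**Conclusion.** The point holds and must be fixed before analysis. Followed as written, 7.5.3 and 7.5.4 estimate survival free of three events, while the endpoint, the sample size and the interim report concern two. This conclusion rests on the text alone and needs no assumption about rates.

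The direction is known: the event-free proportion cannot rise. The size is not known. It may be zero, the documents give neither a rate nor an upper bound, and each patient classified differently is worth 0.72 points.

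**What to change.** **Default.** Delete renal failure at the three places in 7.5.3 and the one in 7.5.4, and record the change in a protocol amendment as section 7.5 requires. The event components then agree with 3.2.1, 7.1, 7.3 and the synopsis. The cost is two words at four places, with no new data.

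Renal outcome can be reported separately from the creatinine and GFR already scheduled. The laboratory summaries and shift tables in 7.7.4 largely provide this for creatinine; GFR is not listed in Table 2 and could be added. Time to normality is not a substitute, because the synopsis limits it to values that are abnormal at baseline: "if abnormal at presentation, will be determined for all subjects".

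**Alternative, if renal failure is meant to count.** Define it, including new onset against baseline. Amend the synopsis, 3.2.1 and 7.3. Restate the expected proportion and the half width that 139 subjects deliver, in the synopsis and 7.1. This costs a definition, rewritten endpoint statements and a new precision statement.

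The deletion aligns event components only. Two other differences need their own reconciliation: the 96-hour time point appears in 7.3, 7.5.3 and 7.5.4 but not in the synopsis endpoint and analysis text, 3.2.1 or 7.1; and the objective in 3.1.1 and the synopsis names hepatic failure or death, which differs from the objective restated in 7.5.3.

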7.5.4 Secondary/Sensitivity Analyses for Primary Endpoints

As a sensitivity analysis, the primary analysis will be repeated using the Per-Protocol Set.

In addition, the survival rates using Kaplan-Meier estimation method at 96 hours (end of treatment period) will be computed for the patients surviving without liver transplantation, renal failure or death. 95% CI will be computed for the survival rate by using Greenwoods formula. This analysis will be carried out using both Full Analysis and Per-Protocol Analysis sets.

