7 STATISTICAL ANALYSIS

7.1 Sample Size Calculations

The overall mortality rate for Legalon® SIL treated patients, regardless of the severity of liver damage, is less than 10%. This represents more than a 50% reduction in the reported mortality rate before Legalon® SIL was available. For ethical and practical reasons there are no controlled clinical studies available for any amatoxin treatments but observational studies and case reports describe successful treatment with intravenous silibinin (Legalon® SIL).

A total of 139 enrolled patients is considered sufficient to show the effect of the Legalon® SIL in preventing liver transplantation, and/or death resulting from amatoxin poisoning. Using the large sample normal approximation, a sample size of 139, provides a two-sided 95% confidence interval for proportion of patients not meeting the outcome of interest (liver transplantation, and/or death) within a half width of 5% from the observed proportion at an expected proportion of 90%.

Published Clinical Experience with Legalon® SIL

Between 1982 and 2008, mostly single cases were published by various authors (Table 7.1). Overall, out of these 1,136 reported patients treated with Legalon® SIL as monotherapy or in combination with mostly penicillin G, 1,064 patients (94%) survived. It was further reported that the severity of liver damage correlated with the time interval between mushroom intake and commencement of silibinin treatment. If silibinin was given within 48 hours after intoxication, a light or medium hepatic injury was expected. When silibinin treatment was delayed by more than 48 hours, then a severe clinical course with coagulation disorders and liver coma was more likely.

Table 3 Summary of Clinical Experience with Legalon® SIL in Amanitin Poisoning

| Reference | Treatment Regimen | No. of Patients | |
|-------------------------------------------------|-------------------|-----------------|----------|
| | | Treated | Survived |
| Lorenz et al. , 1983 (unpublished) | PE + SIL | 201 | 181 |
| Streng-Hesse et al. , 1996 (unpublished) | PE + SIL | 154 | 139 |
| Floersheim et al. , 1982 [29] | PE + SIL | 16 | 16 |
| Hruby 1983 [30] | PE + SIL | 15 | 14 |
| Marugg and Reutter 1985 [33] | PE + SIL | 12 | 11 |
| Smetana et al. , 1986 [34] | PE + SIL | 2 | 2 |
| Schenke et al. , 1987 [35] | SIL | 2 | 2 |
| Hruby 1987 [36] | SIL | 17 | 16 |
| | PE + SIL | 37 | 34 |
| | TH + SIL | 1 | 1 |

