7.5.6 Sub-Group Analyses

The primary and sensitivity analyses of primary endpoint will be repeated by the disease severity stages.

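### The Kaplan-Meier sensitivity analysis names Greenwood's formula but no scale and no rule for strata without events, so its intervals by severity stage can be degenerate or too narrow

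*Combined protocol and SAP*

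**What the plan says.** Section 7.5.3 gives the primary proportion a 95% confidence interval that "will be computed based on Newcombe-Wilson score method". The event is liver transplantation, renal failure or death within 96 hours.

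Section 7.5.4 adds a sensitivity analysis of the same composite, in the Full Analysis Set and the Per-Protocol Set: "the survival rates using Kaplan-Meier estimation method at 96 hours (end of treatment period) will be computed". For its precision, "95% CI will be computed for the survival rate by using Greenwoods formula". It does not say whether the interval is formed on the plain, log or complementary log-log scale.

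Section 7.5.6 then states: "The primary and sensitivity analyses of primary endpoint will be repeated by the disease severity stages". Both the Wilson interval and the Greenwood interval are therefore planned in every stratum. Stratum sizes and stratum event rates are not given, and no rule covers a stratum in which nobody has an event. Section 7.5 leaves detailed methodology to a statistical analysis plan, but the document contains no further text on this point.

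**The concern.** Greenwood's formula gives a variance; an interval also needs a scale. On the plain scale, with nobody censored before 96 hours, the result is the Wald binomial interval, which behaves poorly when the success rate is near 100% and the group is small. The plan does not use that interval for the primary proportion but leaves it open for the sensitivity analysis of the same endpoint.

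The problem is sharpest in the milder strata. Section 2.2 describes widely different prognoses: best in Grades 1 and 2, and a 90% probability of death in Grade 4. If the overall success rate is near the planned 90%, some strata must lie above it, and a stratum with no events is a realistic result. A plain Greenwood interval there has zero width. The sensitivity analysis would then look more certain than the primary analysis of the same patients, purely because of the formula.

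**Working it through.** **Inputs.** From the protocol: n=139 and an expected success rate of 90% with a half width of 5 points (Section 7.1); interim success 42/50 = 84% (Section 7.6); published survival 93%, counting death only (Section 7.1, Table 3). The 90% and 84% figures refer to transplantation or death, not to the composite with renal failure, so they serve only as reference values. Assumed here: strata of 10 to 46 subjects (an equal split over the three stages in Section 2.2 gives 139/3 = 46.3), a rate of 95% for a milder stratum, and no censoring before 96 hours unless stated.

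**1. The plan's own figure.** n = 1.96² × 0.90 × 0.10 / 0.05² = 138.29, rounded up to 139; the half width at 139 is 4.99 points. The stated sample size reproduces.

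**2. Greenwood without censoring.** The variance is S² × Σ d/[r(r−d)], with d events among r at risk. Each term equals 1/(r−d) − 1/r. With x of n subjects event-free the sum telescopes to 1/x − 1/n. Multiplying by S² = (x/n)² gives p(1−p)/n with p = x/n. The plain interval is therefore the Wald interval.

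**3. No events.** The sum is empty, so the variance is zero, with or without censoring. Plain scale: 100% to 100%. Complementary log-log scale: log(−log 1) = log 0, undefined. The Wilson lower limit when all n succeed is n/(n + 1.96²):

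| n | Wilson lower limit | Clopper-Pearson lower limit |
|---|---|---|
| 10 | 72.2% | 69.2% |
| 20 | 83.9% | 83.2% |
| 30 | 30/33.84 = 88.6% | 88.4% |
| 46 | 92.3% | 92.3% |

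**4. Coverage of the plain interval.** This is the sum of the binomial probabilities of all x whose interval contains the true p.

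At n=139: 92.6% at p=0.84, 93.3% at 0.90 and 91.1% at 0.95. Wilson gives 95.1%, 95.2% and 94.7%. The misses are lopsided: the plain interval lies wholly above the true rate in 5.6% of trials at p=0.90 and in 7.9% at p=0.95, against a nominal 2.5%. With 10% to 20% censoring (assumed; 8,000 simulated trials per setting, exponential times), coverage is 93.3% to 94.0% at p=0.90 and 89.6% to 91.6% at p=0.95.

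For assumed stratum sizes, at p=0.90 / 0.95:

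| n | Plain Greenwood coverage | Chance of no events (pⁿ) |
|---|---|---|
| 10 | 65.0% / 40.0% | 35% / 60% |
| 20 | 87.6% / 63.9% | 12% / 36% |
| 30 | 80.9% / 78.2% | 4% / 21% |
| 46 | 94.7% / 90.4% | 1% / 9% |

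Coverage does not rise steadily with n because the binomial is discrete.

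**5. One event.** For 29/30 the plain interval is 90.2% to 103.1%, with an upper limit above 100%. The log-log interval is 78.6% to 99.5%.

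**6. Check of the remedy.** Log-log alone is not enough. If zero-event strata are still printed as 100% to 100%, its coverage at p=0.95 is 72.5% (n=30) and 56.6% (n=20), below the plain interval. With a Wilson interval for zero-event strata, coverage at p=0.90 / 0.95 is 95.2% / 97.1% (n=139), 97.4% / 93.9% (n=30), 95.7% / 92.5% (n=20) and 93.0% / 91.4% (n=10).

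**The case against.** Four objections carry weight.

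- **The plain scale is not in the protocol.** A reader might infer that the plan prescribes plain Greenwood intervals. It does not: it names a variance formula that the log-log interval also uses, and a later analysis plan could settle the scale. This stands. What remains is that the scale is unspecified, so the interval depends on a software setting, and that no choice of scale deals with a stratum without events.
- **The full-set shortfall is small.** A reader might infer serious under-coverage in the main Kaplan-Meier result. At 139 subjects the shortfall is about 2 to 4 points. For 125/139 the plain interval is 84.9% to 94.9% and the log-log interval 83.6% to 93.9%, so the limits differ by about one point. This stands.
- **The severe figures rest on assumptions.** The protocol gives neither stratum sizes nor a 95% success rate. With 46 subjects and a 90% rate, coverage is 94.7%, close to nominal. This stands, and it is why a range is shown. The zero-width result needs no such assumption; only its probability does.
- **A sound interval is already planned in every stratum.** Section 7.5.6 repeats the primary Wilson analysis by stage too. A reader might infer that a report would show only 100% to 100% for a stratum without events; the protocol does not support that. The objection limits the harm but leaves two contradictory intervals for the same patients.

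The protocol also ties no hypothesis test or success threshold to this interval. Section 7.5.7 uses Greenwood's formula for time to normality, but those curves were not examined here and the point does not extend to them.

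**Conclusion.** The point holds in a limited form. Followed as written, Sections 7.5.4 and 7.5.6 give a degenerate interval in any severity stratum without events, whichever of the plain or log-log scales is used. That follows from the formula alone. If the plain scale is chosen and censoring is slight, coverage is modestly low in the full set and can be severely low in small strata: from 94.7% down to 40.0% over the sizes and rates assumed above. The chance of meeting a zero-event stratum ranges from 1% to 60% over the same grid. The consequence is confined to a sensitivity analysis; the primary estimate, its Wilson interval and the sample size are unaffected. It is worth correcting before the analysis plan is final, because an avoidable defect would make the supportive result look more precise than the primary one.

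**What to change.** In Sections 7.5.4 and 7.5.6, or in the analysis plan that details them, state that 96-hour Kaplan-Meier rates are reported with complementary log-log transformed Greenwood intervals. State also that any stratum with no events reports a Wilson or Clopper-Pearson interval instead, and name the denominator to be used if subjects are censored before 96 hours. Both parts are needed, since log-log alone is undefined in a stratum without events.

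The cost is a sentence or two of text and a software option. No data collection, sample size or primary analysis changes. Intervals become wider: hardly so at 139 subjects, but noticeably in small strata, where 29/30 goes from about 13 to about 21 points.
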